The immediate post-intervention effect of CHAMP (compared to control participants) on each SR outcome variable will be evaluated at post-intervention (month 9). We will examine descriptive statistics for both pre- and post-intervention SR measures of the outcome variables for each group. The change in *cognitive flexibility, working memory, behavioral inhibition, and emotion regulation* scores will be compared between the intervention (CHAMP) and control groups using regression models, adjusting for other confounding factors. Random effects will be included in the model to accommodate for the potential within-cluster correlations due to nested classroom data. We anticipate that some children will have only partial adherence to the intervention (i.e. attend a subset of sessions), thus we will also conduct a dose-response analysis where dose corresponds to number of sessions. We will also investigate the amount of attrition from pre- to post-intervention, and attempt to identify baseline (or pre-intervention) predictors of the likelihood of dropping out (as an indication of possible bias in the change estimates).

Aim 2. Test the hypothesis that improvement in child SR indicators (*cognitive flexibility, working memory, behavioral inhibition, and emotion regulation*) is associated with improved motor competence, perceived motor competence, and objectively-measured PA from pre- to post-test.

We will examine strength of association between each SR variable and our outcomes of interest using bivariate analyses to compare change in SR to change in motor competence, perceived motor competence, and PA (using an alpha value of $p < .05$). We will also use multivariate regression models (controlling for covariates as needed) to examine the association of SR and outcomes in each group (CHAMP and control) in order to test whether the strength of association varies by intervention status.

Sample Size, Power Analysis and Sample Attrition. The sample size was calculated based on our findings from preliminary data. After 9 months, we will be able to detect effects between intervention and control groups with 85% power at an alpha level of 0.05, with a total of 98 subjects (49 subjects per arm). To account for a total of a 16.5% loss at post-intervention, we will recruit 120 subjects (60 subjects per arm) at baseline.

Missing Data: Assuming data are Missing at Random (MAR), multiple imputation techniques will be used to replace missing data.⁷⁶ Missing data will be assumed to be MAR if no participant demographics or primary outcomes are correlated with missingness. Mixed effects models allow for partial information to be included for individuals who may dropout prior to any post-intervention data collections. Sensitivity analysis over a range of missing data mechanisms will be performed as necessary. We expect limited missing data because the Michigan research staff will be present to supervise data collection and identify potential problems with missed data. Missing values will be multiply imputed using available covariates by sequential imputation. This approach allows optimal use of available data in analysis involving change measures.

Early Withdrawal/Dropouts: Measures will be taken to retain all participants overtime, however we do expect to loss participants in both the intervention and control groups overtime. A conservative estimate of this attrition rate is 30% during the study period. We plan to implement the intent-to-treat (ITT) analysis.⁷⁷ We will make every effort to collect follow-up data at each time point from individuals who have not withdrawn from the study. Our approach has been to sponsor booster sessions as “classroom reunion/birthday parties” along with rewards and incentives to gather follow-up data. This approach has worked well for bringing kids together to reduce potential dropout.

Data Management. Extreme care to ensure high-quality and secure data will be exercised. All data will be stored securely at the University of Michigan. Data will have only a numerical identifier so that individual respondents cannot be identified from the data. However, it is possible to enter the ID number into the electronic subject database and thereby identify study participants. Thus, we have devised a specific procedure for limiting access to the linking information. All data will be reported as aggregate statistics and no individuals will be recognizable from the data reported. All data will be perused for consistency, errors of omission, and appropriateness of response. Unacceptable responses will be investigated with follow-up questioning, until acceptable answers are obtained. Once a coded and cleaned data file has been prepared, frequency distributions and descriptive statistics (means, standard deviations, and ranges) for each of the measured variables will be used for consistency checks and to verify the comparability of the groups. Logic check programs will be run to ensure that each data point falls within the expected range or corresponds to possible values in the codebook. These tracking system files will be maintained on a secure server at the University of Michigan. Data will be analyzed using SAS 9.3.^{74,76} All members of the study team will be required to complete the web-based University of Michigan Responsible Conduct of Research Training Program and to sign a confidentiality document stating that they understand the procedures to be followed to ensure the integrity and confidentiality of the data and the consequences of disregarding them. Careful training and ongoing monitoring of data collectors will be provided by the Principal Investigator and will follow a set of procedures used successfully in our previous studies.

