Official Title: A PATH (Promoting Activity and Trajectories of Health) for Children

NCT Number: NCT03189862

Document Date: 9/16/2019

IRB Research Plan - HUM00133319

A PATH (Promoting Activity and Trajectories of Health) for Children (Phase I, Cohort 2)
 Science for Behavior Change
 (Based on PROTOCOL HUM0011789)

Ame00094488

The Amendment to HUM00133319 are as follows:

1. Update of [name] affiliation

Objective

a. Objective 1

Physical inactivity in children is a major public health risk factor and national health objective. This National Institutes of Health application 1 R01 HL132979-01 entitled "A PATH (Promoting Activity and Trajectories of Health) for Children" (scored at the 13th percentile) will investigate the immediate and long-term effects of a motor skills - the Children's Health Activity Motor Program (CHAMP) on motor competence, perceived motor competence, and physical activity in preschool-age children. The specific aims are to: 1) examine the immediate post-intervention effect of CHAMP (compared to control participants) on motor competence, perceived motor competence, and physical activity in preschool-age children; 2) assess the sustainable effect of CHAMP (compared to control participants) on motor competence, perceived motor competence, and physical activity across middle childhood; and 3) examine and compare the immediate and long-term mediating effects of perceived motor competence on the relationship between motor competence and physical activity in preschool-age children. We hypothesize that children in CHAMP, compared to control, will demonstrate higher levels of motor competence, perceived motor competence, and physical activity at post-intervention and across the 3-year follow-up. This study will consist of a cluster randomized control trial and CHAMP will be implemented in a predominantly minority and low income population, Head Start preschoolers (N = 300; 3.5-5 years old). Thirty classes of preschool children will be randomly assigned to either the treatment (CHAMP, n = 15) or control (normal preschool free-play/recess, n = 15) condition. The CHAMP intervention will be implemented for (4, 30-minute classes a week or 3, 40-minute classes a week, based on the needs of the school schedule) ~~-30 minutes/day 4 days per week for 30 weeks (~3600 min dose)~~. Data will be collected on: a) 7-day physical activity levels using accelerometry, b) process- and product-oriented motor skill competence c) perceived motor competence.

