
for each child. In CHAMP, children are given opportunities to make choices on specific task engagement, participate in a variety of learning experiences and peer interactions (e.g., cooperative and independent), involve themselves in leadership roles, and are allowed to choose the length of practice time necessary to develop a specific aspect of a skill (i.e., based on personal capabilities).

The CHAMP session is designed to take place in a school gymnasium or large indoor open space (i.e., multipurpose room) that has been designated at each preschool center. The space needed will accommodate 25 – 28 preschool-children and two classroom teachers (i.e., 1 instructor and 1 assistant). For this study, the instructors will be graduate trained movement science specialists. Equipment for the implementation of CHAMP consists of items typically found in preschool movement or early childhood physical education programs or can be obtained for minimal costs (e.g., balls of various sizes, bean bags, cones of various height, striking objects, targets, etc).

Methodology

Research Design. The proposed study is a two arm cluster randomized control trial with follow-up. Classes of children will be randomly assigned to treatment (i.e., movement intervention – CHAMP or the normal movement program provide by their educational center (Control; outdoor free-play activity in a large playground area with a variety of play structures that promote movement and physical activity but no planned instruction nor activities).

Setting and Participants (Recruitment). This study will take place in three Head Start centers (i.e., Perry, Ford, and Beatty) located in Ypsilanti Michigan (Midwest). The racial make-up of the centers are 65.9% Black or African American, 19.14% White (non-Hispanic), 8.82% Hispanic/Latino, 3.26% Asian-Pacific Islander, 2.82 other races (two or more), and 0.06% Native American. Participants will be 300 preschool-age children age 3.5 years and older that encompass diverse settings (30 classes; 15 CHAMP Treatment and 15 Control; 150 preschoolers per condition). Thus, participants will primarily be from urban settings and include low and middle SES black/African American. The three Head Start centers are on the same campus for the three elementary schools (Grades K – 5) where the students will enroll for their formative schooling (i.e., Erickson, Adams Stem, and Holmes Elementary School), which will aid with retention over 3-years of follow-up.

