Upon receiving IRB approval, the consenting process will occur through multiple methods (see below Informed Consenting Methods for specific details). Upon returning the IRB form and to compensate the parent/guardian for their time, parent/guardian will receive a one-time \$5.00 cash incentive. Additionally, fully completed Family Questionnaires will be entered in a drawing to win one (1) of eight (8) \$50.00 Gift Cards to Wal-Mart or Kroger Shopping Center. A random drawing will be used to select four (4) completed surveys from each preschool. The child ID number for each completed survey will be placed in a Choice Picker, random selection software, and selected. Completed Family Questionnaires will be entered in a drawing to win one (1) of eight (8) \$50.00 gift cards to Wal-Mart or Kroger Shopping Center (i.e., 4 for each school). Two (2), \$50 gift card drawings will occur each day (i.e., one (1) for each preschool) and will occur over four (4) consecutive days. ID numbers of completed surveys will enter four discrete pools on each day of the drawing (e.g. Subjects 1-37 on Day One for each site, Subjects 38 - 75 on Day Two for each site,), and Subjects 76-113 on Day Three for each site, Subjects 114-150 on Day 4 for each site). Parents will receive a yearly report regarding their child's assessment findings. Early withdrawal from this study will forfeit future compensation. The decision to use Wal-Mart and Kroger gift card over a Visa/Mastercard gift card was due to cost, location, and variety. These stores do not have a surcharge of \$4.95 – \$6.95 to load funds, there are several locations in the area, and they provide a variety of options for purchase.

Informed Consenting Methods

- 1) **Preschool Registration/Sign Up Day.** The PI and members of the investigative team will be present at the Registration/Sign-Up Day to address any questions from the parent(s) and to discuss the project. Informed consents and Family Questionnaire packets will be available to parents.

The four (4) other steps will be completed to achieve our targeted N.

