The Children's Health Activity Motor Program (CHAMP) Implementation. CHAMP will be implemented during the scheduled movement sessions at each participating preschool (see preschool letters of support, Appendix A). CHAMP consists of (4, 30-minute classes a week or 3, 40-minute classes a week, based on the needs of the school schedule). ~~~30 weeks per year that will equate to ~3600 minutes of intervention time (30 min sessions X 4 days per week X 30 weeks per year)~~. Each session will consist of three parts: (a) 2 -3 min of motor skill introductory activity, (b) 25 min of motor skill instruction and practice, and (c) 2 -3 min motor skill closure activity. The control condition will be the preschools typical activity programs (i.e., outdoor/freeplay recess) and will be implemented according to the existing procedures within the preschool center. The centers outdoor program consist of outdoor free-play activity on a large playground area with a variety of play structures (swings, slides, ladders) that promote gross movement and activity in preschoolers. For the control condition, there will be no planned instruction nor activities provided by the classroom teachers. CHAMP will be implemented by two trained movement science specialists (1 instructor and 1 assistant). Instructors will attend a 3-day (4 hr/day) workshop/training session prior to the start of the intervention. The training workshops will be conducted by [name], an expert in movement/physical activity programming in early childhood settings and the developer of CHAMP. During the training workshops, instructors will learn the theoretical approach of CHAMP, see and actively participate in a CHAMP session and demonstrate effective implementation of the CHAMP intervention. During the training session, instructors must be able to provide a range of cues and prompts to promote skill learning, set up and demonstrate basic task progressions for motor skills, modify tasks based upon the child's present level of performance and rates of improvement, and implement CHAMP with fidelity, appropriate transitions and pacing, while ensuring safety. All training sessions will be digitally recorded and available through a private YouTube channel. A printed manual will also be provided to promote fidelity of the intervention. During the intervention, instructors will wear wireless microphones and digitally record each CHAMP session in order to determine fidelity. Ensuring fidelity demonstrates a measure for the internal validity of CHAMP.⁴⁴ Fidelity will be calculated from the digital recordings using a systematic observation tool established for mastery interventions.⁴⁵ CHAMP fidelity checks will be conducted during week 1, 3, 7, 15, and 25. [name] will deliver fidelity support (additional training) to instructors by providing adjustments to teacher behaviors if CHAMP specialists are not implementing CHAMP with fidelity. Concurrently, during weeks 1, 3, 7, 15 and 25, systematic observations tools at the control site will also occur for additional internal validity.⁴⁶

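### The plan does not state how class randomisation is balanced across the three centres and two yearly cohorts, centre enters the models only as a random effect on three units, and the site wording conflicts

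*Protocol*

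**What the plan says.** **Unit of assignment.** Protocol, Objective 1: "Thirty classes of preschool children will be randomly assigned to either the treatment" or the control condition, 15 classes each. Research Design repeats it: "Classes of children will be randomly assigned to treatment". Neither place mentions stratification, blocking or any other restriction by centre.

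**Centres and years.** Setting and Participants: "This study will take place in three Head Start centers". The note on recruitment numbers under Inclusion/Exclusion Criteria splits enrolment into 150 children in Year 1 (75 per arm) and 150 in Year 2. It gives no class-level allocation rule for either year.

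**Comparator.** Control is "the normal movement program provide by their educational center" (Research Design), and it "will be implemented according to the existing procedures within the preschool center" (CHAMP Implementation).

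**Where each arm is found.** CHAMP Implementation places CHAMP in the movement sessions of every participating preschool, and then says that in weeks 1, 3, 7, 15 and 25 "systematic observations tools at the control site will also occur for additional internal validity". The questionnaire drawing under Informed Consent describes two preschools: two drawings a day, one per preschool, with identification numbers ending at "Subjects 114-150 on Day 4 for each site".

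**Analysis.** Protocol section E and the SAP (Analyses of primary outcomes) recognise clustering by classroom and preschool and plan random effects. The covariates named for the main trial are sex (Protocol, Aim 2) and age and sex (SAP, Aims 1 and 2). Neither document names centre or cohort as a covariate.

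**The concern.** The comparator is each centre's own playground programme, so what CHAMP is compared with may differ from one centre to another. Each centre also shares a campus with the elementary school its children are expected to enter, so a centre difference could persist into the follow-up waves. If the arms are spread unevenly over centres, part of any between-centre difference in change falls into the estimated CHAMP effect on MVPA, motor competence and perceived competence. The usual protection is to balance allocation within centre and include centre in the model. The text states neither, apart from a variance component that would have to be estimated from three centres.

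The site wording adds a second difficulty. A reader cannot confirm from the documents that both arms are present in every centre, or that the control condition is observed wherever it is delivered.

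**Working it through.** **The plan's own figure.** Inputs from Sample Size, Power Analysis and Sample Attrition: difference 12.1 min/day, SD 27, 90% power, alpha 0.05 (taken as two-sided). n per arm = 2 × (1.960 + 1.282)² × 27² / 12.1² = 104.6, so 105; the t-based version gives 106, as stated. For 30% loss, 212 / 0.70 = 303, against 298 stated. The sample size is not in dispute here. It supplies the scale for what follows.

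**Assumptions.** The documents do not give class counts per centre or differences between centres. I assume 10 classes in each centre, classes of equal size, and one centre whose mean MVPA change differs from the other two by Δ = 4 to 12 min/day.

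**Chance of an uneven split.** With 15 of 30 classes drawn for CHAMP without regard to centre, the number K in a given centre is hypergeometric: P(K = k) = C(10,k) × C(20,15−k) / C(30,15).

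- P(K = 7, 8, 9, 10) = 0.0975, 0.0225, 0.0025, 0.0001; the sum is 0.1225.
- A given centre splits 7:3 or worse in either direction: 2 × 0.1225 = 24.5%.
- At least one of the three centres does so (full enumeration): 46.7%. For 8:2 or worse: 12.2%.
- Any centre falls wholly in one arm: 0.06%. Under other assumed class counts this is 1.7% (6/10/14) or 10% (4/10/16).

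**Shift in the unadjusted contrast.** The deviant centre supplies K/15 of CHAMP classes and (10 − K)/15 of control classes, so the shift is Δ × (2K − 10)/15. At 7:3 it is Δ × 4/15:

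| Δ (min/day) | Shift at 7:3 | Share of 12.1 |
|---|---|---|
| 4 | 1.07 | 9% |
| 8 | 2.13 | 18% |
| 12 | 3.20 | 26% |

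The probability that goes with this table is 24.5%, because the deviant centre itself must be the one that splits unevenly. It is not 47%.

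**Over all randomisations.** The mean of K is 5, so the mean shift is zero. Var(K) = 15 × (1/3) × (2/3) × (15/29) = 1.724, SD 1.313. The SD of the shift is Δ × 2 × 1.313 / 15 = 0.175Δ, which is 0.70 min/day at Δ = 4 and 2.10 at Δ = 12. The standard error of the planned comparison, ignoring clustering, is 27 × √(2/106) = 3.71 min/day.

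**Site wording side by side.** Three centres (Setting and Participants) against two preschools (the drawing); CHAMP at every participating preschool against one control site (both in CHAMP Implementation). Neither pair can be true as written.

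**The case against.** The strongest reply is that classes are randomised, so the comparison is unbiased whether or not centre is a stratum. That stands: leaving out stratification costs precision and exposes the trial to chance imbalance, but it does not create systematic bias. Three further points reduce the size. The Aim 1 analysis compares change from baseline, so a stable centre difference in MVPA level cancels and only a difference in change remains. The planned random effects would adjust partly for uneven splits. Control is described in the same terms throughout (outdoor free play, play structures, no planned instruction), and play-space ratings are planned at the beginning and end of the school year, so the weekly observations are not the only information on the control environment.

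A reader might infer something stronger from the singular control site and from two sites with numbers up to 150, since 150 is also the number of children per condition: that whole sites were allocated, so that arm and site are the same thing. The documents do not support this. They state class randomisation twice and place CHAMP in every participating preschool. The drawing concerns a questionnaire, not allocation, and 150 is also the yearly recruitment target. Nor can one say that classes were not randomised within centre: the available text is silent, and part of the protocol was not available to this review.

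What remains is that the allocation rule is unstated, centre is handled weakly, and the site descriptions contradict each other.

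**Conclusion.** The point holds as a modest, inexpensive improvement to design reporting and analysis. Under the stated class randomisation, uneven splits are common (47% for at least one centre at 7:3 or worse), but the consequence is limited: a shift with mean zero and SD 0.7–2.1 min/day, smaller than the comparison's own standard error of about 3.7. In an unlucky draw, with probability 24.5% for a given centre, the shift is 1.1–3.2 min/day at 7:3 and larger for a worse split. All of this rests on 10 equal-sized classes per centre and an assumed centre difference in change of 4–12 min/day, and it applies to the contrast before any adjustment.

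Systematic confounding of arm with centre is not shown. It would require allocation by site, which the documents do not describe. The conflicting site wording only means that the text alone does not let a reader rule it out.

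**What to change.** 1. In Research Design, state that classes are randomised within each centre and each yearly cohort, as near 1:1 as class numbers allow. If assignment is already done, report the arm-by-centre-by-cohort table instead.
2. In the Aim 1 and Aim 2 models (Protocol section E and SAP), fit centre and cohort as fixed effects and keep classroom as a random effect. A fixed centre term does not depend on a variance estimated from three units.
3. In CHAMP Implementation, have the control observations already planned for weeks 1, 3, 7, 15 and 25 cover control classes in every centre that has them.
4. Reconcile the three centres, the two-preschool drawing, the single control site and the delivery of CHAMP at every participating preschool.
5. If the table shows that arm and centre coincide, say so in the conclusions. Fixed effects would then be aliased with arm, and no model adjustment can separate the two.

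The cost is about three degrees of freedom (two for centre, one for cohort), which at class level takes 30 − 2 = 28 down to 25, together with some wording and the spreading of the control observations over the centres.
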